8. MEASUREMENT OF EFFECT

8.1 Antitumor Effect – Solid Tumors (RECIST 1.1)

Although the clinical benefit of these drugs has not yet been established, the intent of offering this treatment is to provide a possible therapeutic benefit, and thus the subjects will be carefully monitored for tumor response and symptom relief in addition to safety and tolerability. Subjects will be assessed by standard criteria for response per the timelines noted in the Study Calendar (Section 10).

Response and progression will be evaluated in this study using the new international criteria proposed by the revised Response Evaluation Criteria in Solid Tumors (RECIST) guideline (version 1.1) [123]. Changes in the largest diameter (unidimensional measurement) of the tumor lesions and the shortest diameter in the case of malignant lymph nodes are used in the RECIST criteria.

In addition, if a formal reading for RECIST measurements is performed, but the results are not available prior to the scheduled start of the next cycle, treatment should continue based upon review of the routine/clinical radiologist report of the status of disease (e.g., response, stability or progression). In the event that a RECIST re-read would have changed the treatment decision for the subject, if known prior, the IND Sponsor/designee should be consulted and course of action

clearly documented in the medical record. If it is in the best interests of the subject to continue on study, this is permissible. These cases will be reviewed in detail at the time of study analyses.

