8.2.2 Methods for Evaluation of Measurable Disease

All measurements should be taken and recorded in metric notation using a ruler or calipers. All baseline evaluations should be performed as closely as possible to the beginning of treatment and

never more than 28 days before the beginning of the treatment. Tumor response will be assessed per RECIST 1.1 using radiographic scans every 8 weeks±7 days.

The same method of assessment and the same technique should be used to characterize each identified and reported lesion at baseline and during follow-up. Imaging-based evaluation is preferred to evaluation by clinical examination unless the lesion(s) being followed cannot be imaged but are assessable by clinical exam.

Clinical lesions: Clinical lesions will only be considered measurable when they are superficial

calipers (e.g., skin nodules). In the case of skin lesions, documentation by color photography, including a ruler to estimate the size of the lesion, is recommended.

Chest x-ray: Lesions on chest x-ray are acceptable as measurable lesions when they are clearly defined and surrounded by aerated lung. However, CT is preferable.

Conventional CT and MRI: This guideline has defined measurability of lesions on CT scan based on the assumption that CT slice thickness is 5 mm (0.5 cm) or less. If CT scans have slice thickness greater than 5 mm (0.5 cm), the minimum size for a measurable lesion should be twice the slice thickness. MRI is also acceptable in certain situations (e.g., for body scans).

MRI has excellent contrast, spatial, and temporal resolution; however, there are many image acquisition variables involved in MRI, which greatly impact image quality, lesion conspicuity, and measurement. As with CT, if an MRI is performed, the technical specifications of the scanning sequences used should be optimized for the evaluation of the type and site of disease. Furthermore, as with CT, the modality used at follow-up should be the same as was used at baseline and the lesions should be measured/assessed on the same pulse sequence.

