8.3.6 Progression-Free Survival

Progression-free survival (PFS) is defined as the duration of time from start of treatment to time of progression per RECIST1.1 or death whichever comes first. PFS for patients who are not progressed at the time of data analysis will be censored on the date of the latest tumor assessment. Patients who go off treatment and begin alternate therapy, prior to progressing on this protocol will be censored at the time on the date of the latest tumor assessment before starting the alternate therapy. We assume that all patients have radiographic scans during screening period and before starting treatment. The following table describes how PFS event is defined and PFS time is calculated. Only radiographic scans used to tumor assessment per RECIST 1.1 before starting the alternate therapy will be counted if patients go off treatment and begin alternate therapy. The following table shows how PFS is defined in various scenarios (*Table 8.3.2*).

Scenario	PFS event (1) or censor (0)	PFS time
At least one post treatment scan is available and tumor response is evaluated according to RECIST 1.1 and all scans are completed on the schedule or off the schedule within a month and patient is alive at the latest follow-up.	1 if PD 0 if no PD	The date of the latest tumor assessment – the date of starting treatment

Table 8.3.2 Definition of PFS

At least one post treatment scan is available and tumor response is evaluated according to RECIST 1.1, but the gap between radiographic scans is greater than 3 months. No PD is observed on the latest scan before the gap occurs.	0	The date of the latest tumor assessment before the gap– the date of starting treatment
No disease progression per RECIST 1.1 is observed on the post-treatment scans and patient dies before the next scheduled scan + 1 month.	1	The date of death – the date of starting treatment
No disease progression per RECIST 1.1 is observed on the post-treatment scans and patient dies. The period from the latest scan to death is greater than 3 months.	0	The date of the latest tumor assessment – the date of starting treatment
No post-treatment scan is available and patient dies before the first scheduled scan + 1 month.	1	The date of death – the date of starting treatment
No post-treatment scan is available and patient is lost follow up or patient dies >3 months later after starting treatment.	0	0

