Electrocardiogram (ECG) ¹¹	Х										

						cycle ** = 28 days)			Maintenance Phase		
Procedure	Baseline ¹	Lead-In Day -14*	Lead-In Day -7	Day 1 (±3 days)	Day 8 (±1 day)	Day 15 (±3 days)	Day 22 (±1 days)	Week 6 (+14 days)	Every 4 weeks, Beginning on week 16***	Every 8 weeks (±7 days) ²	EOT ³ 28 days After Last Dose (±7 days)
Urinalysis ¹²	X										
Pregnancy test/ Assessment WOCBP ¹³	х	X*		X					X		
Tumor Assessments Imaging ¹⁴	Х									X	X ²⁰
CA19-9		X*								x	X ²⁰
Entinostat ¹⁵		x	X	Х	X	Х	х	х	Х		
Nivolumab ¹⁶				х		х		х	Х		
Peripheral blood for PBMC (up to 180cc) ¹⁷		X		х				Х			Х
Peripheral blood for plasma (up to 20cc) ¹⁷		х		х				Х			Х
Serum (up to 10cc) ¹⁷		Х		Х				X			Х
Fresh Tumor Biopsy ¹⁸		х		X ¹⁸				X ¹⁹			X ²⁰
Archival Tumor Sample ²¹	X										
Concomitant Medication Review	X	X		X		X		X	X		X
Symptom/Toxicity Assessment ²²			X	Х		X		X	X ²²		Х

						cycle ** = 28 days)			Maintenance Phase		
Procedure	Baseline ¹	Lead-In Day -14*	Lead-In Day -7	Day 1 (±3 days)	Day 8 (±1 day)	Day 15 (±3 days)	Day 22 (±1 days)	Week 6 (+14 days)	Every 4 weeks, Beginning on week 16***	Every 8 weeks (±7 days) ²	EOT ³ 28 days After Last Dose (±7 days)
Follow-up/Survival ²³											X ²⁴

Study Calendar: Entinostat and Nivolumab

- Baseline evaluations should occur within 28 days prior to registration, unless otherwise noted. NOTE: No window applies to demographics, informed consent, or height at baseline. If any assessments are repeated after registration and prior to dosing on Day -14, subjects must maintain eligibility requirements in order to initiate therapy. Biopsies should be performed only after patient is deemed eligible and registered on the trial.
- ² Disease assessments will be conducted every 8 weeks (+/- 1 week) from Cycle 1 Day1 for the first 6 months; this timeframe may then be extended to every 12 weeks (+/- 1 week) at the discretion of the treating provider.
- ³ A mandatory End of treatment (EOT) visit should be performed 28 days (± 7 days) after the last dose of entinostat to determine patients' safety outcome. Repeat any physical or laboratory assessments after the last dose of any study treatment if last assessment >7 days prior.
- ^{4.} Complete physical exam will be completed at baseline; focused physical examinations may be conducted thereafter.
- ^{5.} Hematology Panel includes at a minimum: basophils, eosinophils, hematocrit, hemoglobin, lymphocytes, monocytes, neutrophils, platelet count, and total white cell count.

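### The fixed 3-month limits in the PFS table do not fit the optional 12-week scan interval, so some on-schedule progressions and some deaths meet a censoring row

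*Combined protocol and SAP*

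**What the plan says.** **Imaging schedule.** Section 8.2.2 calls for "radiographic scans every 8 weeks±7 days" and mentions no later change. Footnote 2 of the Study Calendar (Section 10) begins the same way, "Disease assessments will be conducted every 8 weeks (+/- 1 week) from Cycle 1 Day1 for the first 6 months", and then adds that "this timeframe may then be extended to every 12 weeks (+/- 1 week) at the discretion of the treating provider". Section 8.1 says that patients are "assessed by standard criteria for response per the timelines noted in the Study Calendar".

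**PFS rules.** Four rows of Table 8.3.2 (Section 8.3.6) matter here:

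- First row: scans on schedule, or off it by no more than a month, in a patient alive when last followed up. Progression is an event.
- Gap row: at least one post-treatment scan, no progression on the scan before the gap, and "the gap between radiographic scans is greater than 3 months". The patient is censored, and the time runs to "The date of the latest tumor assessment before the gap".
- Early-death row: no progression seen, and death no later than one month past the next scheduled scan. This is an event.
- Late-death row: no progression seen, and death more than 3 months after the latest scan. The patient is censored at that scan.

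The table does not say which row prevails when two apply. Section 12.3.2 calls for Kaplan-Meier PFS rates at 6, 12 and 24 months.

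**The concern.** Two of these rows set their limit relative to the scan schedule, and two use a fixed 3 months. The two kinds of limit agree when scans are 8 weeks apart. Once a patient moves to 12 weeks they no longer agree, and a patient who is scanned exactly as the protocol permits can fall under a censoring row. An observed progression or death then either counts as an event or is replaced by censoring at an earlier scan, depending on which row the analyst reads first.

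The late PFS rates are at stake. About 27 patients per cohort are planned and fewer will be at risk after 6 months, so one or two reclassified events can shift an estimate visibly.

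**Working it through.** **The plan's own figures.** The documents give no figure for scan gaps or PFS precision. The only design calculation is the Simon design for ORR, and it reproduces. With 13 then 27 patients and rejection at 4 or more responses, power at 20% is 0.801, type I error at 5% is 0.042, and the early-stopping probability is 0.95^13 = 0.513. None of this uses PFS.

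**Inputs.** Intervals of 8 weeks (56 days) and 12 weeks (84 days), each ±7 days (Section 10). The limit is 3 months, which is 89 to 92 days depending on the calendar, or 91.3 on average. One month is 30.4 days.

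**Step 1: possible gaps between compliant scans.** Footnote 2 counts from Cycle 1 Day 1, so each scan has its own window around a fixed date. Then gap = interval + (d2 − d1), with d1 and d2 between −7 and +7.

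| Schedule | Smallest | Nominal | Largest |
|---|---|---|---|
| 8 weeks | 42 | 56 | 70 |
| 12 weeks | 70 | 84 | 98 |

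The 8-week schedule never reaches 3 months. The 12-week schedule exceeds it only when an early scan is followed by a late one.

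**Step 2: how often.** The documents give no distribution of scan days, so I assume independent uniform timing within the window. For a limit of T days, P(gap > T) = (14 − (T − 84))² / (2 × 14²).

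- T = 91.3: 6.7² / 392 = 11.5%.
- T = 92: 36 / 392 = 9.2%.
- T = 89: 81 / 392 = 20.7%.

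Counting whole days (225 pairs) gives 28/225 = 12.4% at 91 days, 21/225 = 9.3% at 92 and 45/225 = 20.0% at 89.

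Two adjacent gaps cannot both exceed 91.3 days, since together they span at most 168 + 14 = 182 days. So 2 × 11.45% = 23% of patients followed for two 12-week intervals would have one.

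**Step 3: the other reading of the window.** If it runs from the previous scan, the largest gap is 84 + 7 = 91 days. The limit is then passed only when the three months total 89 or 90 days. Over 1,461 start dates (four calendar years), 87 give 89 days and 216 give 90, so the average share is (87 × 2/15 + 216 × 1/15) / 1,461 = 1.8%.

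**Step 4: which rows apply to a progression found on a compliant 98-day scan.**

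- Patient still alive: the first row (event) and the gap row (censor) both match.
- Patient later dies: the first row requires the patient to be alive, and both death rows require that no progression was seen. Only the gap row matches, and it censors.

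**Step 5: limits that depend on the schedule against the fixed 3 months.** Nominal interval plus one month is 56 + 30.4 = 86 days on 8 weeks, below 91. On 12 weeks it is 84 + 30.4 = 114 days, about 23 days above. Two overlaps follow on 12 weeks: a death about 91 to 114 days after the last scan is both event and censored, and so is a progression found up to a month late in a living patient. If the last scan was 7 days early, the two limits become 93 and 121 days, so the 8-week overlap is at most a couple of days.

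**Step 6: direction of the effect.** I simulated exponential PFS, with progression dated at the next scan, uniform whole-day timing, a limit of 91.3 days and everyone moved to 12 weeks. The 12-month PFS rate (%) was:

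| Assumed median; first 12-week interval from | No gap rule | All gaps censored | Only progressors censored |
|---|---|---|---|
| 6 months; week 24 | 27.9 | 25.6 | 29.5 |
| 12 months; week 24 | 52.8 | 50.5 | 54.7 |
| 6 months; week 32 | 31.1 | 29.4 | 31.8 |
| 12 months; week 32 | 55.7 | 54.1 | 56.6 |

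Censoring all gaps lowers the estimate. Long gaps tend to follow an early scan, so these patients leave the risk set before later events in the same window are counted. Censoring only progressors removes events and raises it.

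**The case against.** The strongest defence is that the first row already settles the matter: an in-window 12-week scan is on schedule, so progression on it is an event. Section 12.3.2 also defines PFS by the first documented progression and states no gap rule. For living patients this shows that censoring is not dictated, but the gap row still matches and nothing ranks it lower. For patients who later die, the first row does not apply as written. Its condition on being alive may be meant only to separate it from the death rows, but the text does not say so.

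Three stronger readings are tempting and are not supported:

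- A reader might infer that the two schedules flatly contradict each other. Section 8.1 defers to the calendar, and footnote 2 is attached to the calendar's 8-week column. Section 8.2.2 is incomplete, and a reader can work out which schedule governs.
- A reader might infer that the 12-week option by itself triggers censoring. The nominal 84 days does not.
- A reader might infer that late PFS is biased upward. Step 6 shows either sign, depending on how the rule is applied.

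The reach is also limited. The trial is not randomised, so scan frequency cannot distort a comparison between arms, and the PFS analyses are descriptive.

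**Conclusion.** The point holds as a gap in the PFS rules. On the 12-week option, the plan does not determine whether certain progressions and deaths are events.

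- About 11-12% of compliant 12-week intervals exceed 3 months (9-20% across calendar readings), given windows anchored to Cycle 1 Day 1 and uniform timing. The share is about 2% if windows run from the previous scan.
- These shares apply only to patients who are progression-free past 6 months and moved to 12 weeks. The documents do not allow that number to be estimated.
- The death overlap of about 91 to 114 days needs no assumption about scan timing beyond nominal dates.
- The 12- and 24-month PFS rates are exposed. In the simulated cases the 12-month rate moved by about 1 to 2 percentage points, in either direction.

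ORR and the Simon design are unaffected. No event up to month 6 changes status, and the 6-month rate is unchanged when the first 12-week interval starts after month 6. If it starts from the week-24 scan and all gaps are censored, patients censored back to that scan can move the rate by about 1 point (52.8% to 51.6% at an assumed 6-month median).

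This should be corrected before analysis. It does not threaten the primary conclusion.

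**What to change.** 1. Carry the footnote 2 schedule into Section 8.2.2, or cross-refer to it, so that the two passages agree.
2. In the gap row and the late-death row of Table 8.3.2, replace the fixed 3 months with a limit tied to the schedule in force. Two consecutive missed scheduled assessments would do, aligned with the rows that allow one month past the next scheduled scan.
3. State the order of precedence among the rows. Progression on an in-window scan should always be an event, whether or not the patient later dies.
4. Say whether the ±1-week window runs from Cycle 1 Day 1 or from the previous scan.

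The cost is protocol and SAP wording only, with no added scans or patients. Removing the provider's discretion over the imaging interval is not required: once the limits follow the schedule in force, a compliant 12-week patient is classified consistently.

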4.5.2.2 Nivolumab

Nivolumab is a fully human monoclonal immunoglobulin (Ig) G4 antibodies. Subjects should be closely monitored for potential AEs during antibody infusion and potential AEs throughout the study.

Since nivolumab contains only human immunoglobulin protein sequences, it is unlikely to be immunogenic and induce an infusion or hypersensitivity reaction. However, if such a reaction were to occur, it might manifest with fever, chills, rigors, headache, rash, pruritus, arthralgia, hypo- or hypertension, bronchospasm, or other symptoms. All grade 3 or 4 infusion reactions should be reported within 24 hours to the IND Sponsor and BMS and Syndax as an SAE if the criteria are met. Infusion reactions should be graded according to CTCAE (version 4.03) guidelines. Treatment recommendations are provided below and may be modified based on local treatment standards and guidelines as appropriate:

For Grade 1 symptoms: (Mild reaction; infusion interruption not indicated; intervention not indicated).
 Remain at bedside and monitor subject until recovery from symptoms. The following

Remain at bedside and monitor subject until recovery from symptoms. The following prophylactic premedications are recommended for future infusions: diphenhydramine 50 mg (or equivalent) and/or paracetamol 325 to 1000 mg (acetaminophen) at least 30 minutes before additional nivolumab administrations.

• For Grade 2 symptoms: (Moderate reaction requires therapy or infusion interruption but responds promptly to symptomatic treatment [e.g, antihistamines, non-steroidal antiinflammatory drugs, narcotics, corticosteroids, bronchodilators, IV fluids]; prophylactic medications indicated for 24 hours).

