6. ADVERSE EVENTS: LIST AND REPORTING REQUIREMENTS

6.1 Study Drugs

6.1.1 Entinostat

Commonly encountered AEs across clinical studies of entinostat monotherapy in patients with solid tumors included hypoalbuminemia, fatigue, nausea, hypophosphatemia, anemia, and thrombocytopenia. Incidence and severity were dose- and schedule-dependent. In a Phase 2, randomized, placebo-controlled study in patients with lung cancer, in which patients received erlotinib+entinostat or erlotinib+placebo, treatment-emergent adverse events (TEAEs) occurring at a $\geq 10\%$ higher incidence in entinostat-treated patients versus placebo-treated patients included nausea (49% versus 25%); anorexia (40% versus 16%); weight decreased (32% versus 18%); dyspnea (31% versus 18%); vomiting (31% versus 13%); peripheral edema (28% versus 13%); anemia (22% versus 11%); thrombocytopenia (15% versus 3%); hypotension (14% versus 2%); and stomatitis (12% versus 2%). In a Phase 2 study in patients with metastatic melanoma treated with entinostat monotherapy, the most common TEAEs were nausea (39%), hypophosphatemia (29%), pain in extremity (21%), and back pain and diarrhea (each 18%) [122]. Additional clinical experience is summarized in the entinostat IB.

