6.3 Reporting Procedures for All Adverse Events

The Investigator is responsible for ensuring that all AEs observed by the Investigator or reported by patients are properly captured in the patients' medical records and reported on the eCRF. The evaluation time period for all adverse events is from the first dose of the investigational agent to at least 30 days after the last dose of entinostat or nivolumab, or until resolution of all acute toxicities associated with study drug administration, whichever is longer, with the exception of SAEs, which must be documented through 100 days following cessation of treatment, or 30 days after the initiation of a new anticancer therapy, whichever is earlier.

The following AE attributes must be assigned by the Investigator:

• event description (with detail appropriate to the event);

- seriousness;
- dates of onset and resolution;
- severity;
- assessment of relatedness to entinostat and to nivolumab; \Box the action taken.

Laboratory abnormalities: Laboratory abnormalities present at the screening visit will be recorded as pre-treatment signs and symptoms. After study treatment administration, all grade 3 and 4 clinical laboratory results that represent an increase in severity from baseline will be reported as AEs. A grade 1 or 2 clinical laboratory abnormality should be reported as an AE only if it is considered clinically significant by the investigator (induce clinical signs or symptoms or require therapy)

The Investigator may be asked to provide follow-up information, discharge summaries, and extracts from medical records.

If applicable, the study drug relationship will be assessed by means of the question: "Is there a reasonable possibility that the event may have been caused by one of the two drugs based on mechanism of action and/or toxicity profile, or by the combination of entinostat with nivolumab?" The relationship of an AE to the administration of the study drug is to be assessed by the investigator according to the following definitions:

- No (unrelated, not related, no relation): The time course between the administration of study drug and the occurrence or worsening of the adverse event rules out a causal relationship and another cause (concomitant drugs, therapies, complications, etc.) is suspected.

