10. STUDY CALENDAR

Notations/reminders for all calendars:

- Baselines assessments are to be conducted within 28 days of registration unless otherwise noted.
 □ Correlative blood and tissue sample participation is mandatory.
- Additional tests may be performed at the discretion of the treating investigator as per routine practice, or as otherwise clinically indicated.

The schedule should be followed as closely as is realistically possible; the schedule may be modified due to problems such as scheduling delays or conflicts (e.g., clinic closure, vacations, etc.) with the guidance of the IND Sponsor/designee, as appropriate, and will not be reportable as a deviation unless the endpoints of the study are affected.

- * Required \leq 7 days prior to the first dose of entinostat
- ** Required assessment windows during combination treatment for each cycle as noted (e.g., Days 1 and 15 is 3 days, weekly is ±1 day). Assessments on Days 1 and 15 should be completed/reviewed prior to planned nivolumab administration.

- *** After 4 months, nivolumab will be given at a dose of 480 mg fixed dose every 4 weeks (maintenance phase). Therapy may continue with entinostat 5 mg weekly plus nivolumab 480 mg every 4 weeks, until intolerance or progression.
- Patients will be assessed in clinic on D1 of every cycle, and will be contacted by phone weekly, on the weeks entinostat alone is self-administered at home.

Required \leq 14 days prior to the first dose of entinostat

NOTE: All timeframes noted after the lead-in phase refer to duration on combination treatment (e.g., first-restaging should occur after 8 weeks of initiation of combination treatment of entinostat and nivolumab.)

Table 10.1 Study Calendar

						cycle ** = 28 days)			Maintenance Phase		
Procedure	Baseline ¹	Lead-In Day -14*	Lead-In Day -7	Day 1 (±3 days)	Day 8 (±1 day)	Day 15 (±3 days)	Day 22 (±1 days)	Week 6 (+14 days)	Every 4 weeks, Beginning on week 16***	Every 8 weeks (±7 days) ²	EOT ³ 28 days After Last Dose (±7 days)
Informed Consent & Review of Eligibility Criteria	Х										
Medical History & Demographics	Х										
Physical Exam ⁴	X	X#		X				X	X		Х
Vital Signs, Height (only baseline), Weight	х	x		х				X	X		х
ECOG Performance Status	Х	х		х		X		X	Х		х
Oxygen Saturation	Х			х		X		Х	X		Х
Hematology Panel ⁵	Х	x		х		X		х	X ⁶		Х
Chemistry Panel ⁷	X	X		X		X		X	Х		Х
Coagulation Panel ⁸	X										
Thyroid Function ⁹	х			х		х		x	X		х
Hepatitis Serologies ¹⁰	х										

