- ⁶ Patients receiving entinostat in the maintenance phase will have hematology panel (as defined above) checked every two weeks (either in clinic or at home). When done at home, patients will be instructed to send the results to the study team and will communicate the results via fax to the study team
- ^{7.} Chemistry panel includes (if possible): albumin, alkaline phosphatase, total bilirubin [nitrogen if total bilirubin is ≥2xULN (and no evidence of Gilbert's syndrome) then fractionate into direct and indirect bilirubin)], bicarbonate, BUN, calcium, chloride, creatinine, glucose, potassium, total protein, SGOT [AST], SGPT [ALT], sodium, LDH, magnesium, amylase and lipase.
- 8. INR (international normalized ratio), PT (prothrombin time) and PTT (partial thromboplastin time) required at screening and within 30 days of image-guided research biopsies. If patient receives a biopsy at disease progression, the coagulation panel must be completed within 30 days prior to biopsy.

[figure not shown]
- ^{9.} Thyroid function will be assessed by TSH (Thyroid Stimulating Hormone) at baseline and prior to each dose of nivolumab. If abnormal, Free T3 (triiodothyronine) and T4 (thyroxine) should be assessed.
- ^{10.} The following should be assessed at baseline: Hepatitis B surface antigen (HBV sAg) and Hepatitis C antibody (HCV Ab) or Hepatitis C RNA (HCV RNA).
- ^{11.} An ECG is required during screening (prior to starting study treatment), as well as at any other time point when clinically indicated. All 12-lead ECGs should be recorded while the subject is in the supine position. The same method of assessment should be used throughout the study. Twelve-lead ECGs will be obtained after the subject has been resting in a supine position for at least 5 minutes.
- ^{12.} Bilirubin, blood, glucose, ketones, pH, protein, specific gravity, color and appearance. Microscopy should be used as appropriate to investigate white blood cells and use the high power field for red blood cells
- ^{13.} For WOCBP (women of childbearing potential) only. A serum or urine pregnancy testing is required prior to study enrollment/registration, ≤7 days prior to the first dose of entinostat and <24 hours prior to the first dose of nivolumab. After the first dose of nivolumab, an interim history to evaluate any risk of exposure to a fetus must be done prior to each dose in lieu of routine HCG testing, if appropriate.

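### The scheduled chemistry panel does not include phosphate, although the protocol names hypophosphatemia as a common entinostat toxicity

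*Combined protocol and SAP*

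**What the plan says.** **Named toxicity.** Section 6.1.1 says that the common adverse events across entinostat monotherapy studies in solid tumors "included hypoalbuminemia, fatigue, nausea, hypophosphatemia, anemia, and thrombocytopenia". It then cites a phase 2 melanoma study of entinostat alone in which hypophosphatemia, at 29%, was second only to nausea at 39%.

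**Scheduled chemistry.** Footnote 7 of the Study Calendar opens "Chemistry panel includes (if possible): albumin, alkaline phosphatase, total bilirubin", continues with calcium, chloride, bicarbonate and BUN, and closes "creatinine, glucose, potassium, total protein, SGOT [AST], SGPT [ALT], sodium, LDH, magnesium, amylase and lipase". Table 10.1 marks this panel at Baseline, Day -14, Day 1, Day 15, Week 6, every four weeks in maintenance, and at end of treatment.

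**Use of the results.** Section 6.3 requires that "all grade 3 and 4 clinical laboratory results that represent an increase in severity from baseline will be reported as AEs". Section 12.3.2 lists clinical chemistry and vital signs among the safety data. It adds that a baseline and at least one post-dose value may be required before a patient enters the analysis of a given safety parameter.

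**Vital signs.** The row "Vital Signs, Height (only baseline), Weight" in Table 10.1 is marked at Baseline, Day -14, Day 1, Week 6, in maintenance and at end of treatment. The Day 15 cell is blank, although nivolumab is marked on Day 15. For the infusion itself, Section 4.5.2.2 says "Subjects should be closely monitored for potential AEs during antibody infusion".

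**The concern.** Safety and tolerability is the first secondary objective (1.2.1). A laboratory toxicity is counted reliably only if the analyte is drawn on a schedule, with a baseline and a known number of patients tested. The protocol tells the reader to expect hypophosphatemia with one of its two drugs, yet its panel covers sodium, potassium, calcium and magnesium and leaves phosphate out without giving a reason.

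If the calendar is followed as written, phosphate values will come only from tests that an investigator chose to order, often because of symptoms. Such tests give a numerator without a defined denominator. Many patients would have no baseline against which the Section 6.3 rule could judge worsening, and some values could drop out under the inclusion condition in 12.3.2. The reported rate would then reflect who was tested as much as who was affected.

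**Working it through.** The plan states no figure for this point, so there is none to reproduce. The check is a comparison of sections and two counts.

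**1. Common entinostat toxicities against scheduled tests.** Section 6.1.1 lists six common events. Fatigue and nausea are clinical. The other four are laboratory findings:

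| Common laboratory toxicity (6.1.1) | Scheduled test | Where |
|---|---|---|
| Hypoalbuminemia | Albumin | Footnote 7 |
| Anemia | Hemoglobin | Footnote 5 |
| Thrombocytopenia | Platelet count | Footnote 5 |
| Hypophosphatemia | None | Not in footnote 7 or any other calendar row |

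Three of the four are covered. Footnote 7 names 18 analytes: 3 in its opening words, 4 in the middle (calcium, chloride, bicarbonate, BUN) and 11 in the closing run. The only similar-sounding item is alkaline phosphatase, an enzyme, which does not measure phosphate.

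**2. Possible size.** Inputs are the 29% rate (6.1.1), 27 evaluable patients per cohort and up to 33 enrolled per cohort (12.2). That the melanoma rate carries over is an assumption. Expected number with the event = rate × patients.

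| Patients | At 29% | At half that rate (14.5%) |
|---|---|---|
| 27 (one cohort) | 0.29 × 27 = 7.8 | 0.145 × 27 = 3.9 |
| 54 (both cohorts) | 0.29 × 54 = 15.7 | 0.145 × 54 = 7.8 |
| 66 (maximum, 2 × 33) | 0.29 × 66 = 19.1 | 0.145 × 66 = 9.6 |

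The half-rate column shows only how the count moves if the rate is lower here. Section 6.1.1 itself says that incidence depended on dose and schedule. No grade breakdown accompanies the 29%, so I read it as any grade. The number at grade 3-4, to which the automatic reporting rule in 6.3 applies, cannot be calculated.

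**3. Vital signs at nivolumab infusions.** The cycle is 28 days (4.1), with nivolumab every two weeks for 16 weeks (footnote 16). Infusions fall at weeks 0, 2, 4, 6, 8, 10, 12 and 14, so there are 16 / 2 = 8.

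- Vital signs scheduled: C1D1, C2D1, C3D1, C4D1, and Week 6, which footnote 17 equates with C2D15. That is 5 of 8.
- Not scheduled: C1D15, C3D15 and C4D15. That is 3 of 8 (38%).
- If the Week 6 visit moves later within the +14 day window in its column header, C2D15 may also be uncovered, making 4 of 8.

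**The case against.** The strongest reply is that nothing prevents a phosphate test. Section 10 lets the investigator order further tests, footnote 7 describes what the panel includes without calling the list complete, and symptom and toxicity review is scheduled throughout. This stands as far as it goes: the supportable statement is that phosphate has no protocol-scheduled measurement. A reader might infer that hypophosphatemia will go unmeasured, that severe cases will not be detected, or that the trial will report it as rare or absent. The documents do not support any of these, because discretionary testing or symptoms may bring cases to light. But discretionary testing does not supply a common baseline or denominator.

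The second reply concerns size, and it also stands. The 29% comes from one melanoma study. In the randomized lung study in the same section, hypophosphatemia is not among the events listed with an excess of at least 10% over placebo. Under 6.3, grade 1-2 laboratory changes are adverse events only if clinically significant. The 8 of 27 is therefore not a count of reportable adverse events lost.

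Two further inferences fail:

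- The combination would look safer than entinostat alone. No such comparison is planned.
- An electrolyte rule in Section 5.1 is left unable to operate. That item is an exception to delaying nivolumab and does not trigger action.

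On vital signs, a reader might conclude that infusion reactions or hypotension go unmonitored. The calendar notes say that Day 1 and Day 15 assessments are completed before nivolumab, so a Day 15 mark would add a pre-dose value and would not detect an infusion reaction. Section 4.5.2.2 covers monitoring during infusion. The 14% versus 2% hypotension figure is from entinostat plus erlotinib, and vital signs are still scheduled at other visits. Physical examination is also blank on Day 15, so the gap may be deliberate.

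Finally, the drug-administration, dose-adjustment and pharmaceutical sections (4.4, 5.1.1, 5.1.3, 7) are largely blank in this copy and could contain further monitoring. The vital-signs point in particular is established against the calendar only.

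**Conclusion.** The phosphate point holds. The calendar schedules a test for three of the four laboratory toxicities that the protocol calls common with entinostat, and none for the fourth. The consequence is limited: asymptomatic hypophosphatemia may be missed, and its rate may be under-reported in the safety analysis.

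On the assumption that the 29% any-grade rate carries over, about 8 of 27 patients per cohort (about 16 of 54 overall) would have an event that no scheduled test would show. The grade 3-4 share is unknown.

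The vital-signs gap is a minor inconsistency in the calendar: 3 of the first 8 nivolumab infusions, or 4 if Week 6 is late, have no scheduled pre-dose vital signs. Both points concern the completeness of secondary safety data. The response-rate endpoint, the two-stage rule and the sample size are untouched.

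**What to change.** Add phosphate to the footnote 7 panel, at baseline and at each visit where the panel is already drawn. This is one more analyte on an existing sample and needs no extra visit. The small downside is more recorded laboratory adverse events. If the omission is deliberate, say so in the protocol, and state in the safety report that phosphate was tested only at discretion, with the number of patients tested.

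As a secondary edit, reconcile the vital-signs row of Table 10.1 with the infusion visits: either mark Day 15 or state that pre-dose vital signs are intentionally not collected then. A mark costs one routine measurement at a visit already attended. It should not be presented as a means of detecting infusion reactions. Both are calendar edits for the next amendment, and neither changes a dose or a management rule.
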